## **9.0 MONITORING UNTOWARD EFFECTS ASSOCIATED WITH OR RESULTING FROM STUDY**

Site staff must first follow their own IRB's procedure for reporting and managing untoward effects.

There are three types of untoward effects to be identified: (1) those related to the participant, (2) those related to the site visits by mystery shoppers, and (3) those related to the neighborhood/community (*if applicable*).

First, the study will catalogue any untoward effect related to the participant. Reporting is required for occurrences including social harms, psychological distress, and serious life threatening events such as suicide attempts. These may be immediately apparent to the study staff, such as the participant's emotional upset state requiring referral for counseling; or they may be delayed and reported later to study staff, such as physical harm to an individual for having participated in the study. Study staff will notify the team of these untoward effects using the iTech QNS accessible through the iTech website (<https://itechnetwork.org>). Study staff will be briefed during the training on the scope of possible untoward effects and instructed to report events.

Second, mystery shoppers may encounter untoward events during sessions that personally affect them. Training and guidance will seek to minimize this risk. Nonetheless, an assessment of the cost of conducting this study must include cataloguing these events as well. The protocol chairs should be notified of these events so that they may be immediately addressed, evaluated, and guidance modified or expanded to minimize similar risk to other study staff.

Third, this community-based study intends to evaluate its impact in site-level service delivery, including unexpected effects of the project on the community. This will be done both formally (through in-depth interviews) and informally through community dialogues with ATN sites, with untoward events being reported to the protocol team.

## **10.0 STATISTICAL/ANALYTIC CONSIDERATIONS**

### **10.1 Introduction**

10.1.1 We will test the efficacy of GC in increasing HIV-negative or HIV-unknown YMSM's successful uptake of HIV and STI testing (e.g., routine HIV/STI testing) and increase in PrEP awareness and willingness, as compared to the attention-control condition over a 12-month period. Descriptive statistics of the psychosocial and demographic characteristics of the participants will be described for all and by intervention group. These will be compared between treatment groups using t-tests or Wilcoxon rank sum tests for continuous variables and chi-square tests for categorical variables. To test for intervention efficacy, we will conduct primary

analyses of our primary outcomes using regression analyses to compare our treatment group to the control using the appropriate link function (identity for continuous outcome, logit for binary outcome, and natural log for count outcomes). The regression will be run with group assignment only in the model, as well as, controlling for participants' socio-demographic characteristics, ATOD and psychological distress, and intervention-related process data (e.g., frequency of use, acceptability). Interactions between group assignment and these characteristics will be tested to explore potential moderators of treatment effect. We will repeat these analyses for the secondary outcomes (e.g., theoretical mediators)).

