## STUDY ABSTRACT

- DESIGN:** *A two-arm prospective randomized controlled trial (RCT) in Philadelphia, Houston, and Atlanta. Participants randomized to the control condition will only see the site locator portion of the Get Connected intervention website. It will include information on HIV prevention services. Participants randomized to the intervention condition will receive tailored online content specific to their demographic characteristics (e.g., age, race/ethnicity, location, and relationship status), HIV/STI risk behaviors (e.g., HIV/STI testing history; substance use; communication with partners regarding status) and sociocultural context (e.g., homelessness, incarceration). We will also recruit, enroll, and train 10-15 mystery shoppers per city to conduct a mystery shopper assessment. Two mystery shoppers will visit each testing site separately and complete a standardized assessment of their visit. Site directors from 10 randomly selected testing sites in each city will be interviewed to assess sites' satisfaction with the biannual performance assessments and their improvements in service delivery when working with YMSM.*
- DURATION:** *Mystery shoppers are enrolled for approximately six months, or the time it takes them to complete approximately ten site visits. YMSM participating in the RCT are enrolled for 12 months.*
- SAMPLE SIZE:** *Total study sample size is 480 with the aim of maintaining a randomized sample of approximately 400 online-recruited and retained YMSM for 12 months. After consent, but prior to completion of the baseline survey, YMSM are randomized to either the intervention (n=240) or control (n=240) condition.*
- POPULATION:** *Individuals who were assigned male at birth and currently identify as male. 15-24 year-old (inclusive), self-report as HIV-negative or sero-status unaware, speak and read English, live in Philadelphia, Houston, or Atlanta, and meet one or both of the following high risk criteria: have not received HIV testing in past six months and/or report having consensual anal sex with a man in the past six months.*
- STRATIFICATION:** *Each site (Houston, Atlanta, and Philadelphia) will enroll 160 YMSM and 10-15 mystery shoppers.*

**DATA  
COLLECTION:**

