**OBJECTIVES**

*To test the efficacy of an e-Health intervention for increasing HIV-negative or HIV-unknown YMSM's successful uptake of HIV and STI testing willingness (e.g., routine HIV/STI testing) and PrEP awareness and willingness, as compared to the attention-control condition over a 12-month period.*

*To examine the quality of HIV test counseling and PrEP-related referrals to YMSM within local HIV/STI testing sites in 3 cities (Houston, Philadelphia, and Atlanta) through the use of mystery shoppers*

*Qualitatively assess testing sites' satisfaction with the biannual performance assessments and their improvements in service delivery when working with YMSM across the three regions.*

Study Design or Schema

Per the diagram above, the study is a two-arm randomized controlled trial. Once participants are proven eligible and they have provided informed consent, they will be randomized to one of two arms: intervention (Get Connected) and control (site locator portion of Get Connected). Participants randomized to the control condition will only have access to the site locator portion of Get Connected, with information on HIV prevention services. Participants randomized to the intervention condition will receive tailored online content specific to their demographic characteristics (e.g., age, race/ethnicity, location, and relationship status), HIV/STI risk behaviors (e.g., HIV/STI testing history; substance use; communication with partners regarding status), and sociocultural context (e.g., homelessness, incarceration). Five study assessments (surveys) are conducted at months 1, 3, 6, 9, and 12 for a total of 12 months follow-up for each arm.

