### 2.4 Study Hypotheses/Research Questions

- *Relative to the control condition, YMSM exposed to the GC intervention will report significantly greater increases in routine HIV/STI testing over a 12-month period. HIV testing will be the primary outcome for the trial.*
- *Relative to the control condition, YMSM exposed to the GC intervention will report increases in motivation around HIV testing (conceptualized as HIV/STI testing intentions, self-efficacy to engage in HIV/STI testing, and overcoming testing-related barriers).*
- *Relative to the control condition, YMSM exposed to the GC intervention will report significantly greater PrEP awareness and willingness to use PrEP).*

The primary analyses of the data from the Get Connected 2-parallel group randomized clinical trial will be performed according to the participants' original treatment assignment (i.e., intention-

to-treat analyses) and the inclusion of all data from all participants randomized in the final analysis.

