### **Binary outcomes such as HIV testing:**

The percentage of participants who report routine HIV testing over a 12-month period will be compared between the intervention arms (GC and the Control condition). Five assessments will occur at 1 month (visit window  $\pm$  1 month), 3 months ( $\pm$  1 month), 6 months ( $\pm$  1 month), 9 months ( $\pm$  1 month), and 12 months ( $\pm$  1 month). Repeated-measures analyses for HIV testing will be implemented by performing a generalized estimating equations (GEE) analysis via the SAS GENMOD Procedure (version 9.4; SAS Institute, Cary, NC) with an exchangeable correlation structure for the repeated measures within participant (binomial-logit model). The statistical model will include three predictors (intervention arm, time on study and the statistical interaction between intervention arm and time on study). The statistical model will provide estimates of the percentages of participants reporting HIV testing (plus 95% confidence intervals) by intervention arm and time on study. The model-based estimates are unbiased with unbalanced and missing data, so long as the missing data are non-informative (missing completely at random, MCAR). A P value  $\leq 0.05$  will be considered statistically significant for the main effects (intervention and time on study) and for the intervention by time on study interaction effect from the repeated measures analysis. **The statistical test for interaction between time on study and intervention arm will be the primary overall hypothesis test to determine whether HIV testing in the intervention groups changed in significantly different ways during follow-up (i.e., different temporal patterns over time).** If HIV testing rates in the two intervention groups are consistently different or similar (i.e., no statistical interaction) then the main effect test for intervention will be used as the primary test of intervention efficacy. If a significant interaction is detected, then Wald chi-square tests will be used to compare the differences between the model-based HIV testing estimates at each time interval and to compare differences over time within each intervention arm. Specific statistical tests will be done within the framework of the generalized linear model. All statistical tests will be 2-sided and unadjusted for multiple comparisons.

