- *Intervention Acceptability:* At each follow-up, YMSM will report data on the acceptability of their assigned arm. We will also use the Systems Usability Scale to ascertain participants' overall satisfaction with the intervention, perception of the information quality, and perceived usefulness of their intervention to improve their health.
- *Use of Intervention over time:* We will measure intervention exposure using paradata

(e.g., process data emerging from use of the WebApp) from backend database of the intervention website, including counts of user sessions, session lengths, pages visited, and functions utilized. This information will assist in examining whether intervention dosage influences the overall efficacy of the intervention, and inform the cost analysis and wider implementation and scalability.

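### Section 10.1 puts a regression that controls for post-randomisation use and acceptability under its primary efficacy analyses, unranked, although it does not estimate the effect of assignment

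*Combined protocol and SAP*

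**What the plan says.** Section 10.1 (Introduction to the statistical section) says that efficacy will be tested by primary analyses of the primary outcomes using regression. The model is run with group assignment only and also with an adjustment set: socio-demographics, "ATOD and psychological distress, and intervention-related process data (e.g., frequency of use, acceptability". The two versions are given without an order of precedence. The adjusted version is not called secondary, supportive or exploratory, and section 2.4 is not mentioned.

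Section 6.1.2 says how the process data arise. On acceptability: "At each follow-up, YMSM will report data on the acceptability of their assigned arm". On use: "We will measure intervention exposure using paradata", meaning back-end WebApp records such as sessions, their length and pages visited. The content behind these measures differs by arm. The Study Abstract states: "Participants randomized to the control condition will only see the site locator portion of the Get Connected intervention website". The design schema repeats it: "Participants randomized to the control condition will only have access to the site locator portion of Get Connected".

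Section 2.4 sets the principle that the primary analyses "will be performed according to the participants' original treatment assignment" and include everyone randomised. For repeated binary outcomes it says "The statistical test for interaction between time on study and intervention arm will be the primary overall hypothesis test" and, without an interaction, "then the main effect test for intervention will be used as the primary test of intervention efficacy". That model has three terms: arm, time and their interaction. The frequent-tester rate is compared by an unadjusted pooled Z-test.

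Section 10.3.1 adds a generalised linear mixed model with a covariate term that is indexed by subject and visit and not otherwise defined. Section 10.3.2 places engagement (acceptability, use over time) in a secondary analysis, as a possible modifier.

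**The concern.** Use and acceptability are consequences of assignment. If the tailored site works by being used, adjusting for use subtracts that part of its effect from the arm coefficient. There is a second problem even if use does nothing. A motivated participant may both use the site more and test more. Among participants with equal use, those in the arm with less to draw them in are then the more motivated, and the arm comparison is no longer the randomised one. Acceptability has the further difficulty that the two arms are rating different things.

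The primary label is what makes this matter. A report written from 10.1 could present the process-adjusted coefficient as a primary efficacy result, or choose between two conflicting primary results once both are known.

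**Working it through.** **Timing.** Randomisation follows consent and precedes the baseline survey; WebApp access comes after that survey (sections 5.1 and 5.3). Use and acceptability can exist only after that. Both are post-randomisation in both arms.

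**Design point.** Section 10.2 states 400 participants for 13 points, 80% power, two-sided 0.05, two-sample test of proportions. It gives no control rate. Per arm, with p̄ the mean of the two rates,

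n = [1.96·√(2p̄(1−p̄)) + 0.8416·√(p1(1−p1) + p2(1−p2))]² / 0.13².

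- 20% v 33%: (1.2233 + 0.5196)²/0.0169 = 179.7, so 180 per arm, 360 in all.
- 25% v 38%: (1.2876 + 0.5474)²/0.0169 = 199.3, so 200 per arm, 400 in all.
- 30% v 43%: (1.3345 + 0.5678)²/0.0169 = 214.1, so 215 per arm, 430 in all.

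A 25% control rate reproduces the stated 400 and is assumed below. The odds ratio for assignment is (0.38/0.62)/(0.25/0.75) = 1.84, log 0.609.

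**Attenuation.** Suppose a share f of the log odds ratio is carried by use. With use held fixed, roughly (1−f)·0.609 remains: odds ratios 1.84, 1.58, 1.36, 1.16 and 1.00 for f = 0, 25, 50, 75 and 100%. A simulation agrees. It used 6,000 trials per cell and 200 per arm, with use normal (SD 1) and shifted by 0.5, 1 or 2 SD in the intervention arm. The model was logit P = a + direct·arm + g·use, calibrated to 25% v 38%, with no confounding. Ranges are over the three shifts.

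| Share carried by use | Adjusted odds ratio | Power, adjusted arm term | Power, unadjusted Z-test |
|---|---|---|---|
| 0% | 1.84–1.86 | 51–78% | 80–81% |
| 25% | 1.58–1.61 | 31–55% | 80–81% |
| 50% | 1.35–1.40 | 16–29% | 80–81% |
| 75% | 1.17–1.21 | 8–12% | 80–81% |
| 100% | 0.99–1.00 | 5–6% | 80–81% |

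At 0% the estimate is not attenuated, but precision is lost because use is correlated with arm.

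**Spurious effect under a true null.** Let motivation m be standard normal, use = max(0, 1 + 2·arm + 0.8m + e) with e standard normal, and let m raise the log odds of testing by 0.4 per SD. Neither arm nor use affects testing. Ignoring the floor at zero, the slope of m on use given arm is 0.8/(0.8² + 1) = 0.488. At fixed use, the intervention arm is therefore lower in m by 2 × 0.488 = 0.976, which gives a log odds ratio of about −0.976 × 0.4 = −0.39. With one million simulated participants the arm log odds ratio was −0.01 unadjusted and −0.39 adjusted. In a separate set of null scenarios at N = 400 (linear probability model, 2,000 replicates), the adjusted estimate ran from −2.5 to −10 points and rejected in 8% to 53% of trials.

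**Where it does no harm.** If the intervention does not raise use, adjustment changes little: a direct log odds effect of 0.3 gave 0.28–0.29 unadjusted and 0.29–0.30 adjusted.

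**The case against.** The strongest reply is that the plan has already fixed its deciding tests. Section 2.4 names them, restricts the longitudinal model to arm, time and their interaction, and uses an unadjusted Z-test for frequent testing. Section 10.2 powers an unadjusted comparison. Section 10.1 also runs the arm-only model and lists it first. The surrounding text gives process data another role: the next sentence of 10.1 speaks of exploring moderators, 6.1.2 speaks of whether dosage influences efficacy, and 10.3.2 treats engagement as secondary. All of this stands, and it limits the point. It does not remove it, because none of these places reclassifies the adjusted regression in 10.1.

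Three stronger readings are tempting, and the documents do not support them.

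- A reader might infer that the trial's deciding efficacy test is contaminated. It is not: no process variable enters the 2.4 tests. That observation concerns process data only and is not a general endorsement of the 2.4 procedure, which is not examined here.
- A reader might infer that the adjusted model could drop randomised participants who lack survey data. Section 10.4 allows complete-case analysis only when few cases are missing and otherwise calls for imputation, and the baseline survey is taken at the enrolment visit.
- A reader might infer that substance use and distress are meant as follow-up values. Both are defined under the baseline heading of 6.1.1. Section 10.1 merely omits the word, which is a wording gap.

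**Conclusion.** The point holds for the adjusted regression in 10.1. It sits under the primary efficacy analyses without rank, and its arm coefficient does not estimate the effect of assignment. It should be corrected, but it does not undermine the tests that 2.4 says will decide.

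Only the mechanism is established, not the size. The control rate, the shift in use, the share of effect carried by use and the role of motivation are all assumptions. Across them the result runs from no attenuation, through complete loss of a real 13-point effect, to a false negative effect where none exists. To say that the model will understate the benefit would go too far: that requires the intervention to raise use and use to carry benefit, and the documents give no data on either.

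**What to change.** - **Section 10.1:** delete intervention-related process data from the efficacy regressions. State that the arm-assignment tests named in 2.4 decide efficacy, and that any covariate-adjusted model is supportive and uses baseline-survey values only. (That survey follows randomisation but precedes WebApp access.)
- **Section 10.3.1:** limit the covariate term of the efficacy mixed model to baseline-survey values in the same way. As written, its visit index leaves a second route for process data to enter.
- **Section 10.3.2:** keep use and acceptability in the secondary engagement analysis, labelled as not an estimate of the intervention effect.

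The cost is a few sentences. No new data are needed, and the engagement question stays in 10.3.2.

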## 10.2 Power Estimates

10.2.1 The primary outcomes for the proposed trial are HIV-negative and HIV-unknown YMSM's successful uptake of HIV and STI testing willingness (e.g., HIV/STI testing), and PrEP awareness and willingness. For HIV testing, we define power as correctly identifying the difference in the proportion of YMSM who engage in HIV testing 2 or more times at least 3 months apart in the 12-month follow-up period ("frequent tester") in our treatment arm (GC) vs. our attention-control arm. For STI testing, we define it as receiving at least one STI test during the 12-month follow-up period. For proportions (e.g., HIV testing; PrEP awareness), our sample size calculations are based on a two-sample test of proportions using a two-sided significance level of 0.05. In order to have 80% power to compare GC to the attention-control group, we require at least 400 participants to find an absolute difference of 13% in cross-sectional analyses. Assuming within-person correlation of 0.25, we can detect an 8.8% difference. A less favorable within-person correlation of 0.75 allows us to detect an 11.3% difference.

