The primary assessment for a difference between intervention arms for 'frequent tester' rates will be a two-sided Z-test for independent proportions with pooled variance. Confidence intervals (95%) will also be reported for the observed difference between the GC and control arms in 'frequent tester' rates. The same analysis plan described above will be used for the other primary outcomes that as binary (i.e., STI testing, PrEP awareness).

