We will use SurveyGizmo to collect YMSM's data. *At baseline, participants will be logged into the SurveyGizmo assessment by site study staff. For follow-up assessments, participants will receive a unique link which will allow them to complete the surveys in multiple sittings or to resume a survey that has timed out or been closed.* Online surveys allow participants to complete the survey at a convenient location, circumvent barriers (e.g., scheduling, transportation) present in interviewer-administered or phone-based interviews, and decrease social desirability. To maximize completion rates, participants will receive email and/or text reminders that a survey is available. Although we will employ recommended strategies to avoid loss to follow-up, we project a conservative attrition of 20%. In the pilot study, we achieved >80% retention using the approaches proposed here.

Secondary objective:

- **Phase 2a: Enrolling and Training of Mystery Shoppers**  
We will enroll and train 10-15 mystery shoppers per city to conduct the mystery shopper assessments. This approach follows best practices indicating that youth involvement is vital when designing relevant and appropriate HIV interventions for the target population. As study staff, we will work with the ATN site in each city to enroll HIV-negative YMSM (ages 18-24) who are interested in serving as mystery shoppers. We will employ a stratified purposive sampling strategy to ensure age and racial/ethnic diversity across mystery shoppers. Of the 10-15 mystery shoppers in each city, we will attempt to recruit diversity in age and race/ethnicity. Mystery shoppers will be 18 to 24 years old (inclusive).
- **Phase 2b: Site Visits**  
Based on feedback from agency directors in our original study, we will send all agency directors a letter informing them of their site's selection for the study before the mystery shopper visits and contact information to reach the research PIs if they have questions about the procedures. Shoppers will be instructed to report that they do not have income or health insurance and do not possess any proof of identification. In so doing, we will be able to ascertain whether these would be potential barriers to testing at a given location and determine the lowest possible fees that would be charged to a YMSM.
- **Phase 2c: Integration of Scores into GC Console**  

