### 3.3 Sample Size

For the primary objective, the research activities involve enrolling a sample of 480 HIV negative or status unaware YMSM (15-24 years), with the aim of maintaining a randomized sample of approximately 400 online-recruited YMSM over 12-months.

For the secondary objective, the research activities involve enrolling a sample of 30-45 HIV negative YMSM (18-24 years), with the aim of visiting each city's public testing sites twice - two mystery shoppers will visit each testing site (i.e., the same shopper will not go to the same testing site twice).

For the tertiary objective, the research activities involve enrolling a sample of 10 HIV testing site directors per city, with the aim of conducting a semi-structured qualitative in-depth interview.

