### 6.1.2 On-study Evaluations/Measures

- *HIV Testing:* Follow-up surveys will repeat the HIV testing questions in each follow-up survey. The HIV testing outcome will be: the proportion of MSM tested for HIV two or more times at least 3 months apart in the 12-month follow-up period (“frequent tester”). As an additional analysis, we will also examine the proportions of participants who receive one HIV test.
  - Among self-reported newly diagnosed HIV+ cases, we will measure their linkage and engagement with appropriate medical care after initial diagnosis using criteria employed in prior ATN protocols with youth. We will define linkage as an HIV-related medical visit within 45 days of referral, and engagement as a second HIV-related medical visit within 16 weeks of initial visit. Onset of ART initiation, self-reported adherence to ART, and viral suppression are exploratory indicators, as we recognize that our follow-up period may not be a sufficient amount of time to see these changes.
- *STI Testing:* The STI testing outcome is defined as the proportion of YMSM tested for STIs at least once in the 12-month follow-up period. We will ask participants what STIs they have been tested for, the anatomic sites where they were tested, the date of their most recent STI test (if known), and whether a medical provider had diagnosed them with an STI. In the follow-up surveys, we will ask participants whether they had been tested for STIs in the past 3 months (for the 1-month follow-up survey, we ask about the past 30 days). If STI testing is reported, we will ask participants to indicate what tests they received, and whether they were diagnosed with an STI by a medical provider.
- *PrEP Use:* At each follow-up assessment, PrEP-eligible HIV-negative YMSM (per CDC guidelines) will be asked whether they have begun using PrEP. We will also ascertain if a provider recommended PrEP and/or were offered a prescription for PrEP.
 

*Site Evaluations:* Across both trial arms, YMSM who report testing in the prior 3 months will complete self-evaluation forms of their testing experiences to assess comfort, quality, and concerns after visiting a site for HIV/STI testing and PrEP prevention services. The assessment form is the same form used by the mystery shoppers. We will use these data to update the WebApp and to send aggregate data of YMSM's satisfaction with services to agencies biannually.

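### Section 10.2 requires at least 400 participants, but the plan's own 20% attrition leaves 384, and its 8.8% and 11.3% figures are not limited to visit-level analyses

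*Combined protocol and SAP*

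**What the plan says.** Section 10.2 (Power Estimates) uses a two-sample test of proportions at a two-sided 0.05 level and 80% power. Its sample size statement is "we require at least 400 participants to find an absolute difference of 13% in cross-sectional analyses". It gives no control or intervention rate.

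The Study Abstract and Section 3.3 set enrolment at 480, 240 per arm; Section 3.3 adds "with the aim of maintaining a randomized sample of approximately 400 online-recruited YMSM over 12-months". Section 3.1, Phase 1c, says "we project a conservative attrition of 20" per cent.

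Section 10.2 defines power for HIV testing on the frequent-tester outcome, which Section 6.1.2 gives as "the proportion of MSM tested for HIV two or more times at least 3 months apart in the 12-month follow-up period". For the second testing outcome it says: "For STI testing, we define it as receiving at least one STI test during the 12-month follow-up period". Section 2.4 states that the primary comparison of frequent-tester rates "will be a two-sided Z-test for independent proportions with pooled variance".

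Directly after the 13% figure, Section 10.2 continues: "Assuming within-person correlation of 0.25, we can detect an 8.8% difference", and then: "A less favorable within-person correlation of 0.75 allows us to detect an 11.3% difference". It does not say which outcomes, how many visits or what base rate these two figures describe.

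**The concern.** Two statements in the power section do not fit the rest of the plan.

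First, 400 is set as a minimum, yet the plan's own enrolment and attrition leave fewer than that.

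Second, frequent tester and any STI test over 12 months each give a single result per participant. With one result per person there is no within-person correlation to exploit, so only the cross-sectional figure can apply. The 8.8% and 11.3% figures nevertheless follow the definitions of these outcomes with no restriction. A reader could conclude that the trial has 80% power for 8.8 or 11.3 points on the outcome that Section 10.2 itself uses to define power. At many control rates it would fall well short of that.

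**Working it through.** **Inputs.** Two-sided alpha 0.05, 80% power, 400 participants and 13 points (Section 10.2); 1:1 allocation (Section 5.3); 480 enrolled (Section 3.3); 20% attrition (Section 3.1). The control rate p1 is not stated, so every value of it below is an assumption. Write d for the difference, p2 = p1 + d, and p̄ for their mean.

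**1. Reproducing the 400.** With the pooled-variance test,

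n per arm = [1.960·√(2p̄(1−p̄)) + 0.842·√(p1(1−p1) + p2(1−p2))]² / d².

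At p1 = 0.25, p2 = 0.38 and p̄ = 0.315 the two roots are 0.657 and 0.650. This gives n = 199.2, rounded up to 200 per arm, or 400 in total. The same formula gives totals of 254 at a 10% control rate, 430 at 30% and 460 at 40%. So 400 fits a control rate of about 25%, or its mirror value of about 62%.

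**2. Attrition.** 480 × 0.80 = 384, or 192 per arm, which is 16 short. 400/480 = 83.3%, so keeping 400 allows at most 16.7% attrition.

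Power = Φ{[d√n − 1.960·√(2p̄(1−p̄))] / √(p1(1−p1) + p2(1−p2))}.

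For 13 points at p1 = 0.25:
- n = 200: (1.838 − 1.288)/0.650 = 0.847, power 80.1%.
- n = 192: (1.801 − 1.288)/0.650 = 0.790, power 78.5%.

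The detectable difference at 80% power moves from 12.97 to 13.26 points. With 192 per arm it is at most about 14.3 points at any control rate (the maximum is near 43%). Over control rates of 10% to 45%, power for 13 points is 94% down to 74% with 400 participants, and 93% down to 72% with 384.

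**3. Within-person correlation and a once-per-person outcome.** For the average of m equally correlated visits, the variance is multiplied by (1 + (m−1)ρ)/m. With m = 1 this equals 1 for any ρ, so neither 0.25 nor 0.75 changes the detectable difference.

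**4. Power for 8.8 and 11.3 points on such an outcome, 200 per arm, p1 = 0.25.**
- d = 0.088: roots 0.644 and 0.641; (1.2445 − 1.2628)/0.6413 = −0.029, power 49%.
- d = 0.113: roots 0.652 and 0.647; (1.5981 − 1.2779)/0.6471 = 0.495, power 69%.

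| Assumed control rate | Power, 8.8 points | Power, 11.3 points | Total N for 80%, 8.8 points | Total N for 80%, 11.3 points |
|---|---|---|---|---|
| 10% | 71% | 88% | 498 | 324 |
| 25% | 49% | 69% | 840 | 522 |
| 45% | 42% | 62% | 1,012 | 614 |

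With 400 participants, 80% power is reached for 8.8 points only at control rates up to about 7% or from about 84%, and for 11.3 points only up to about 15% or from about 74%.

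**The case against.** On attrition, the plan has good answers. It calls 20% conservative. The Study Abstract and Section 3.3 aim for approximately 400, and 384 is within 4% of that. Section 3.1 cites more than 80% retention in the pilot, and Section 8.2 more than 90% in ongoing studies with the same compensation; 90% of 480 would be 432. Section 2.4 plans to include all data from all randomized participants, and Section 10.4 allows imputation of missing endpoints, so 384 need not be the analysed number. All of this stands and may well justify a lower projection. But 20% is the projection on the page, and Section 10.2 words 400 as a minimum.

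On the two smaller figures, the 13% is labelled cross-sectional and the next sentence turns to within-person correlation, so a statistician would take 8.8% and 11.3% as repeated-measures figures. Section 2.4 does plan a per-visit GEE for HIV testing and extends that plan to STI testing and PrEP awareness. This also stands, and it is the most natural reading. What remains is that Section 10.2 does not state the restriction, while the outcomes it has just defined are the ones to which the figures cannot apply.

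A reader might go further and infer that 8.8% and 11.3% are miscalculated. The documents do not support that, because the inputs are not given. For example, 200 per arm for the cross-sectional figure, 240 per arm and three visits for the repeated-measures figures, and an assumed 56.5% control rate give 13.5, 8.8 and 11.3 points. That does not show what the team did, but it rules out calling the figures wrong.

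**Conclusion.** The point holds as an inconsistency in the power statement, minor in size. At the plan's own attrition, 384 remain against a stated minimum of 400. At an assumed 25% control rate this costs under two points of power and about 0.3 points of detectable difference. The 8.8% and 11.3% figures cannot describe frequent tester or any STI test over 12 months. Taken that way with 400 participants, they would carry about 49% and 69% power at a 25% control rate.

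These sizes rest on assumed control rates, on the pooled two-proportion formula and on 1:1 allocation. The impossibility of a gain from within-person correlation does not depend on the control rate.

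Two stronger readings should be resisted. The shortfall of 16 does not make the trial materially underpowered; the unstated control rate moves power far more. Nor does the missing control rate show that 400 is wrong: it is reproduced at about 25%.

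**What to change.** In Section 10.2, wording only:

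1. Restate the evaluable number as 384 with its matching detectable difference: about 13.3 points if the control rate is 25%, and at most about 14.3 at any rate. Alternatively, change the projected attrition to 16.7% or less, in Section 3.1 as well, citing the retention data already in Sections 3.1 and 8.2.
2. State that 8.8% and 11.3% apply only to visit-level repeated-measures analyses. State that for frequent tester and for any STI test over 12 months only the cross-sectional figure applies.
3. When restating, give the control rate and the number of visits used. The visit count needs stating because Section 2.4 lists five follow-up assessments and Section 10.3 refers to baseline and four follow-ups.

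The cost is a few sentences. Enrolment, outcomes and tests stay as they are.
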